1.4. Population, Route, Dosage, Dosage Regimen, Treatment Period

The study population will be adult (age \geq 18 years) male and female subjects with a CrCl between 15-59 mL/min, and a diagnosis of FM for up to 5 years prior to screening.

Subjects must meet specific pain criteria at the Screening and Randomization Visits for inclusion. Full details regarding eligibility criteria are provided in Section 4.

The dosage form of DS-5565 drug product is white oval 7.5 mg tablets. The tablet formulation includes DS-5565 drug substance, mannitol, carboxymethylcellulose calcium, magnesium stearate, and Opadry®OY-S-9607 (a pre-mixed powder for coating suspension containing hypromellose, titanium dioxide, and talc). The tablets will be orally administered. Study treatment may be taken with or without food once in the morning and once in the evening. Matching placebo tablets will also be used.

Full details regarding study treatment are provided in Section 5.

1.5. Compliance Statement, Ethics, and Regulatory Compliance

This study will be conducted in compliance with the protocol, the ethical principles that have their origin in the Declaration of Helsinki, the International Conference on Harmonisation (ICH) consolidated Guideline E6 for Good Clinical Practice (GCP) (CPMP/ICH/135/95), and applicable regulatory requirement(s) including:

- Food and Drug Administration (FDA) GCP Regulations: Code of Federal Regulations (CFR) Title 21, parts 11, 50, 54, 56, and 312 and/or
- European Commission Directive (2001/20/EC Apr 2001) and/or
- European Commission Directive (2005/28/EC Apr 2005) as appropriate.

1.5.1. Subject Confidentiality

The Investigators and the Sponsor will preserve the confidentiality of all subjects taking part in the study, in accordance with GCP and local regulations.

The Sponsor will observe the rules laid down in the European Data Protection Directive 95/46/EC on the protection of individuals with regard to the processing of personal data and the free movement of such data.

The Investigator must ensure that the subject's anonymity is maintained. On the Electronic Case Report Forms (eCRF) or other documents submitted to the Sponsor or designee, subjects should be identified by a unique subject identifier as designated by the Sponsor. Documents that are not for submission to the Sponsor or designee (eg, signed Informed Consent Forms [ICF]) should be kept in strict confidence by the Investigator.

In compliance with applicable regulations and ICH GCP Guidelines, it is required that the Investigator and institution permit authorized representatives of the Sponsor, of the regulatory agency(s), and the Independent Ethics Committee (IEC) or Institutional Review Board (IRB) direct access to review the subject's original medical records for verification of study-related procedures and data. The Investigator is obligated to inform the subject that his/her study-related records will be reviewed by the above named representatives without violating the confidentiality of the subject.

1.5.2. Informed Consent Procedure

Before a subject's participation in the study, it is the Investigator's responsibility to obtain freely given consent, in writing, from the subject after adequate explanation of the aims, methods, anticipated benefits, and potential hazards of the study and before any protocol-specific screening procedures or any study drugs are administered. The written ICF should be prepared in the local language(s) of the potential subject population.

In obtaining and documenting informed consent, the Investigator should comply with the applicable regulatory requirements, and should adhere to GCP and to the ethical principles that have their origin in the Declaration of Helsinki. The consent form and any revision(s) should be approved by the IRB/IEC prior to being provided to potential subjects.

The subject's written informed consent should be obtained prior to his/her participation in the study and should be documented in the subject's medical records, as required by law. The ICF should be signed and personally dated by the subject, and by the person who conducted the informed consent discussion (not necessarily the Investigator). The original signed ICF should be retained in accordance with institutional policy, and a copy of the signed consent form should be provided to the subject or legal representative. The date and time (if applicable) that informed consent was given should be recorded on the CRF.

Suggested model text for the ICF for the study and any applicable subparts are provided in the Sponsor ICF template for the Investigator to prepare the documents to be used at his or her site. Updates to applicable forms will be communicated via letter from the Sponsor.

Additional consent is required for the Health Insurance Portability and Accountability Act (HIPAA) only in the USA.

1.5.3. Regulatory Compliance

The study protocol, subject information and consent form, the Investigator Brochure, any subject diary card or written instructions to be given to the subject, available safety information, subject recruitment procedures (eg, advertisements), information about payments and compensation available to the subjects, and documentation evidencing the Investigator's qualifications should be submitted to the IRB/IEC for ethical review and approval according to local regulations prior to the study start. The written approval should identify all documents reviewed by name and version.

Changes in the conduct of the study or planned analysis will be documented in a protocol amendment and/or the Statistical Analysis Plan (SAP).

The Investigator must submit and, where necessary, obtain approval from the IRB/IEC for all subsequent protocol amendments and changes to the informed consent document or changes of the investigational site, facilities, or personnel. The Investigator should notify the IRB/IEC of deviations from the protocol or serious adverse events occurring at the site and other adverse event reports received from the Sponsor or designee, in accordance with local procedures.

As required by local regulations, the Sponsor's local Regulatory Affairs group will insure all legal aspects are covered and approval of the appropriate regulatory bodies obtained, prior to study initiation, and that implementation of changes to the initial protocol and other relevant study documents happen only after the appropriate notification of or approval by the relevant regulatory bodies.

2. STUDY OBJECTIVES AND HYPOTHESES

2.1. Study Objectives

2.1.1. Primary Objective

The primary objective is to determine the safety and tolerability of subjects with FM and moderate to severe renal dysfunction during 13 weeks of renally adjusted dosing of DS-5565 compared to placebo.

2.1.2. Secondary Objectives

The secondary objectives of this study are:

- To compare change in weekly average daily pain as assessed by ADPS from baseline measured at randomization to Week 13/ET in subjects receiving either dose of DS-5565 versus placebo. Weekly ADPS is based on daily pain scores reported by the subject that best describes the worst pain over the previous 24 hours
- To assess the effects of DS-5565 on patient global impression of change (PGIC) at Week 13/ET.

2.2. Study Hypothesis

The hypothesis of this Phase 3 study is that doses of 7.5 mg BID of DS-5565 in subjects with CrCl between 30-59 mL/min and 7.5 mg QD of DS-5565 in subjects with CrCl between 15-29 mL/min DS-5565 will be safe and well tolerated.

[figure not shown]
3. STUDY DESIGN

3.1. Overall Plan

3.1.1. Study Type

This is a stratified, randomized, double-blind, placebo-controlled, multi-center safety study of DS-5565 for the treatment of pain due to FM in subjects with CrCl between 59 and 15 mL/min. The study design is depicted in Figure 3.1.

Figure 3.1: Design of Phase 3 Study of DS-5565 in Subjects with FM

3.1.2. Treatment Groups

Subjects who meet all eligibility criteria will be randomized 2:1 to receive either DS-5565 7.5 mg QD or placebo for the category of subjects with CrCl 15-29 mL/min, or 2:1 to receive treatment with DS-5565 7.5 mg BID or placebo for the category of subjects with CrCl 30-59 mL/min.

Matching placebo will be utilized to conduct the double-blind treatment period.

The Schedule of Events is listed in Section 17 and the Study Procedures in Section 6.

3.1.3. Study Endpoints

The primary safety endpoint is the safety and tolerability of renally adjusted doses of DS-5565 versus placebo.

Specific safety endpoints assessed include:

- All treatment-emergent adverse events (TEAEs)
- Change in clinical laboratory evaluations from baseline measured at randomization to Week 13/ET for DS-5565 versus placebo
- Change in neurological examinations from baseline to Week 13/ET for DS-5565 versus placebo
- Change in electrocardiograms from baseline to Week 13/ET for DS-5565 versus placebo
- Change in Columbia-Suicide Severity Rating Scale (C-SSRS) from baseline to Week 13/ET for DS-5565 versus placebo
- Assessment of Physician Withdrawal Checklist (PWC) at follow-up visits.

The secondary efficacy endpoints include:

- Changes in ADPS from baseline measured at randomization to Week 13/ET for DS-5565 versus placebo. Weekly ADPS is based on daily pain scores reported by the subject that best describes the worst pain over the previous 24 hours.
- Proportion of subjects with improvement in overall status at Week 13/ET as assessed by PGIC for DS-5565 versus placebo.

3.1.4. Duration of the Study

3.1.4.1. Duration of Subject Participation

The total study duration (for individual subject's participation) will be approximately 21 weeks. The study includes a screening period (approximately 3 weeks but no longer than 35 days, including a washout period [if necessary] and a 1-week baseline period), double-blind treatment period (13 weeks), and a 4 week follow-up period.

3.1.5. Stopping Rules

3.1.5.1. Stopping Rules for Individual Subjects

For any subject discontinued from the study based on one of the stopping rules outlined in Section 3.1.5.1.1, the associated event must be reported as an adverse event (AE) or serious AE (SAE) in the eCRF within 24 hours of awareness. Please refer to Section 9.4 for further instructions.

3.1.5.1.1. Elevations of Aminotransferases

Although a mechanism- or metabolism-based potential for drug-induced liver injury has not been established for DS-5565, instances of increased hepatic transaminases have been observed during the development program. In addition, acetaminophen, an agent known to cause liver injury (due to saturation of its metabolism when overdosed), is commonly used in this population and is included in this study as an allowed treatment for pain. As such, a standardized approach for stopping rules and careful monitoring of serum transaminases is considered prudent. Stopping rules for elevation in serum transaminases are included as a general precaution, with attention to FDA guidance for detection and assessment of drug-induced liver injury premarketing clinical evaluations, and are described below. Specific recommendations regarding monitoring of subjects with elevations are described in Section 9.3.2.

Subjects with any of the following elevations in aminotransferases should be discontinued from treatment and followed closely, as noted above.

- Increase in alanine aminotransferase (ALT) or aspartate aminotransferase (AST) ≥ 5 x upper limit of normal (ULN)
- ALT or AST increases to ≥ 3 x ULN and persists for more than 2 weeks
- Concurrent increases in ALT or AST ≥ 3 x ULN and total bilirubin ≥ 2 x ULN
- ALT or AST ≥ 3 x ULN associated with a clinical presentation suggestive of liver injury (i.e., including the appearance of fatigue, nausea, vomiting, right upper quadrant pain or tenderness, fever, rash, and/or eosinophilia)

3.1.5.2. Suicidal Behavior and Ideation

The α,δ ligand class of medications has been associated with increased risk of suicidal thoughts or behavior (Section 9.3.1). Two separate cases of completed suicide were observed in the Phase 2 DS5565-A-J202 study.

The C-SSRS and Mini-international Neuropsychiatric Interview (MINI) (Version 6.0) are to be administered at any time during the study (including unscheduled visits) where the investigator/study coordinator/site staff recognizes or become aware of (and this includes if this awareness arises during unscheduled visits or non-face-to-face communications with the patient or his/her family):

- Any suggestion of mood disturbance and/or any awareness of a potential suicidal risk,

- Substantial changes in their psychosocial environment (ie, the death of or separation of close family/friend, sudden financial burden, worsening of medical condition, etc); in this case administration of the C-SSRS/MINI and consultation with a psychiatrist (onsite preferably) should be performed.

In this study, the C-SSRS will be administered at all clinic visits. Based on the C-SSRS and Investigator judgment, if a subject is identified as being at risk for suicide, appropriate safety measures should be implemented, including:

- A subject should be discontinued from the study, and immediately referred to a mental health professional for further evaluation, if a 'YES' response has been recorded for any question on the C-SSRS at any visit (current or past), unless the subject falls into the 'Possible Exception' category below.
 - Possible Exception (with regard to a 'YES' response(s) to C-SSRS Q1 and/or Q2 only):
 1. The benefit from continuation on the study medication significantly outweighs the risk of continuing the subject on study drug. Such cases need to be discussed with the sponsor medical director and should take into account the mental health professional evaluation AND
 2. The justification for continuing the subject in the study under these circumstances is to be appropriately documented per study procedure

Subjects should be discontinued from the clinical study and immediately referred to a mental health professional (preferably an onsite psychiatrist evaluation if possible) if subjects are assessed as having current severe or uncontrolled major depressive disorder or anxiety disorders by the MINI at any visit (current or past) and if any of the following conditions apply:

- The investigator determines that there is a suicidality risk, irrespective of any scales or
- Any "Yes" response to:
 - MINI questions
 - Module A (Major Depressive Disorder) question A3, G or
 - Any question on Module B (Suicidality) or
 - Relevant C-SSRS questions, with discontinuation criteria as outlined above.

3.1.5.3. Decreased CrCl Below Minimum

If at any time during the study the CrCl drops below 15 mL/min, the subject must be discontinued from the study utilizing the stated withdrawal procedures and referred to a nephrologist.

3.1.5.4. Stopping Rules for the Study

Circumstances under which the study may be stopped based upon independent Data and Safety Monitoring Board (DSMB) recommendation are specified in Section 11.9. In addition, the study may be terminated at any time at the Sponsor's discretion.

3.2. Selection of Doses

3.2.1. Experimental Treatments for the Study

Dose regimens were selected based on results of single-dose studies in healthy volunteers, as well as dose optimization modeling and simulation. At doses from 3 to 75 mg, DS-5565 was rapidly absorbed, with a median time to maximum plasma concentration (t_{max}) of approximately 1 hour. Mean $t_{1/2}$ ranged from approximately 3 hours to 5 hours, and C_{max} and AUC appeared to increase proportionally with doses from 3 mg through 75 mg. The majority of administered DS-5565 is excreted in the urine (approximately 61% to 77% of the dose). The overall exposure to DS-5565, based on AUC, increased with severity of renal impairment.

In the completed Phase 2, randomized, double-blind, placebo- and pregabalin-controlled study of DS-5565 in subjects with DPNP in the US (DS5565-A-U201), the primary efficacy endpoint was met. Greater mean decreases from baseline to end-of-treatment (Week 5) in ADPS were observed in the DS-5565 treatment groups compared to placebo. The mean changes from baseline to Week 5 (with last observation carried forward imputed for missing values) in ADPS were -2.0, -2.3, -2.7, -2.6, and -2.8 for the DS-5565 5 mg QD, 10 mg QD, 15 mg QD, 10 mg BID, and 15 mg BID treatment groups, respectively. By comparison, placebo and pregabalin showed mean changes of -1.9 and -1.8, respectively.

DS-5565 has been shown to be generally well-tolerated at single doses up to 30 mg. The most frequently reported TEAEs are CNS-related events that are expected based on the mechanism of action of DS-5565 and included high rates of dizziness and somnolence. Most reported TEAEs were judged to be mild or moderate, and most were considered to be related to the study drug. In the completed Phase 2 study (DS5565-A-U201), all DS-5565 dose levels were generally well tolerated.

DS-5565 has been studied in subjects with renal dysfunction. Study E106 evaluated the PK and safety of a single 5 mg dose in 40 subjects (8 subjects with normal renal function and 8 subjects each with mild, moderate, severe, and ESRD, respectively). Pharmacokinetics of DS-5565 and its lactam metabolite were evaluated over a 72-hour period. For the analysis, the groups were analyzed by normal CrCl (≥ 90 mL/min), mild reduction in CrCl (60 to 89 mL/min), moderate reduction in CrCl (30 to 59 mL/min), and severe reduction in CrCl (15 to 29 mL/min).

The PK analysis indicated that there was a significant reduction in both CL_r/F and CL/F of DS-5565 and its lactam metabolite as renal function decreased (Table 3.1).

Table 3.1: Renal and Total Clearance of DS-5565 and its Lactam Metabolite with Decreasing Renal Function

CrCL (mL/min)	N	CL/F (L/hr)	
		Observed Median (Min, Max)	Predicted Median (Min, Max)
≥ 90	6	20.0 (12.7, 23.2)	18.9 (10.7, 22.9)
60-89	8	17.4 (8.94, 20.5)	17.2 (9.28, 19.5)
30-59	10	8.04 (6.90, 11.3)	8.01 (7.21, 11.2)
15-29	4	4.73 (3.80, 5.75)	4.81 (3.83, 5.95)
<15	4	3.76 (2.75, 5.98)	3.87 (2.82, 5.76)

CrCl = creatinine clearance; CL/F = total clearance

In subjects with moderate and severe renal dysfunction BID doses of 7.5 mg and QD dosing of 7.5 mg are expected to produce exposures equivalent to a BID doses of 15 mg in subjects with normal renal function (Table 3.2).

Table 3.2: Predicted DS-5565 AUC with Daily and Twice Daily Doses of 7.5-15 mg in Renal Dysfunction

CrCl Group (mL/min)	Dose	AUC _{ss,0-24h} (ng*h/mL)		C _{max,ss} (ng/mL)	
		Mean	Median	Mean	Median
≥ 90	15 mg BID	1834	1590	241	252
60-89	15 mg BID	1958	1747	238	226
30-59	7.5 mg BID	1754	1873	161	152
15-29	7.5 mg QD	1586	1563	157	165

AUC = area under the plasma concentration-time curve; AUC_{ss,0-24h} = area under the plasma concentration-time curve at steady state from 0 to 24 hours; C_{max,ss} = maximum plasma concentration at steady state; CrCl = creatinine clearance; BID = twice daily; QD = once daily

3.2.1.1. Experimental Treatment for Individual Subjects

There will be no dose adjustments.

3.2.2. Control Treatments

Placebo will serve as the control treatment. Inclusion of placebo is required in light of the known placebo effect in pain studies.

4. STUDY POPULATION

4.1. Enrollment

Investigators will maintain a confidential screening log of all potential study candidates that includes limited information of the subjects (initials, age, sex) date and outcome of screening process (eg, enroll in the study, reason for ineligibility, refused to participate).

Prior to initiation of formal screening procedures, each subject will be asked to review and sign the ICF provided by the site. All subjects must personally sign and date the ICF before any study-specific activities occur. For additional information on informed consent, see Section 1.5.2.

Each subject will be assigned a unique subject identification number (SID) upon signature of the ICF at the Screening Visit. The SID will be an 8-digit number with the first 4 digits corresponding to the site number and the last 4 digits as sequentially assigned by the interactive voice/web response system (IXRS). The SID will be used to identify the subject throughout the study and will be entered on all study documentation. If a subject discontinues from the study at any time, his/her SID cannot be reassigned to another subject.

Investigators will maintain a confidential subject identification code list. This confidential list of names of all subjects allocated to study numbers on enrolling in the study allows the Investigator to reveal the identity of any subject when necessary.

A subject will be considered enrolled upon being randomized into the study. Investigators will maintain an enrollment log of all subjects enrolled in the study, indicating their assigned study number.

4.1.1. Inclusion Criteria

Subjects must satisfy all of the following criteria to be included in the study:

1. Age \geq 18 years
2. Able to give written informed consent
3. Able to complete patient-reported questionnaires per the Investigator's judgment
4. Estimated CrCl between 15-59 mL/min from serum creatinine by the central laboratory using the Cockcroft-Gault equation
5. Fibromyalgia meeting American College of Rheumatology criteria for FM:
 - a. Widespread pain index (WPI) \geq 7 and symptom severity (SS) scale score \geq 5, or WPI 3 to 6 and SS scale score \geq 9,
 - b. Pain in at least 11 of 18 specific tender point sites,
 - c. Symptoms have been present at a similar level for at least 3 months, and
 - d. The subject does not have a disorder that would otherwise explain the pain

6. ADPS of ≥ 4 on the 11-point numeric rating scale (NRS) over the 7 days prior to randomization (based on completion of at least 4 daily pain assessments during the 7-day baseline period prior to randomization)
7. Women of child bearing potential (WOCBP) must be using adequate methods of contraception (as detailed in Section 4.1.3) to avoid pregnancy during the study and for 4 weeks after study completion.

4.1.2. Exclusion Criteria

Subjects who meet any of the following criteria will be disqualified from entering the study:

1. Need for ongoing use of concomitant chronic pain medications or any new non-pharmacological pain management techniques that may confound assessments of efficacy and/or safety, including neurolytic treatments (destruction of nerves by chemicals, heat, cold) or surgery, intrathecal pumps, spinal cord stimulators or psychological support within the previous year. Also excluded: topical capsaicin within 6 months; or systemic corticosteroids within 3 months of baseline period.
2. Unable to undergo pre-study washout of prohibited concomitant medications
3. Subjects with recent history (ie, within 1 year prior to screening) of alcohol abuse or illicit drug use (cocaine, heroin, marijuana [including medical, prescribed], etc.)
4. Use of any selective serotonin reuptake inhibitor (SSRI), unless the subject has been on a stable dose for ≥ 90 days prior to screening and is not anticipated to need any dose adjustment during the course of the study
5. Subjects with severe or uncontrolled depression that, in the judgment of the Investigator, makes the subject inappropriate for entry into the study
6. Significant neurological or psychiatric disorder unrelated to neuropathic pain
7. Other severe pain (eg, sciatica, rheumatoid arthritis) that might impair the assessment of neuropathic pain
8. $\text{CrCl} \geq 60$ mL/min estimated from serum creatinine by the central laboratory using the Cockcroft-Gault equation.
9. Subjects who are on hemodialysis or who require hemodialysis before the follow-up assessment; acute renal failure; history of kidney transplant
10. Any history of a malignancy other than basal cell carcinoma within the past 5 years
11. Clinically significant unstable neurologic, ophthalmologic, hepatobiliary, respiratory, or hematologic illness or unstable cardiovascular disease (eg, severe hypotension, uncontrolled cardiac arrhythmia, or myocardial infarction) within 12 months prior to screening
12. Pregnancy or breast feeding or intent to become pregnant during the study period

13. Known hypersensitivity to $\alpha_2\delta$ ligands or other components of the study medications. Note: Prior exposure to DS-5565 is allowed, as long as hypersensitivity to DS-5565 was not observed.
14. Clinically significant ECG abnormalities at the Screening Visit

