2. Unable to undergo pre-study washout of prohibited concomitant medications
3. Subjects with recent history (i.e., within 1 year prior to screening) of alcohol abuse or illicit drug use (cocaine, heroin, marijuana [including medical, prescribed], etc.)
4. Use of any selective serotonin reuptake inhibitor (SSRI), unless the subject has been on a stable dose for ≥ 90 days prior to screening and is not anticipated to need any dose adjustment during the course of the study
5. Subjects with severe or uncontrolled depression that, in the judgment of the Investigator, makes the subject inappropriate for entry into the study
6. Significant neurological or psychiatric disorder unrelated to neuropathic pain
7. Other severe pain (eg, sciatica, rheumatoid arthritis) that might impair the assessment of neuropathic pain
8. $\text{CrCl} \geq 60$ mL/min estimated from serum creatinine by the central laboratory using the Cockcroft-Gault equation.

-
9. Subjects who are on hemodialysis or who require hemodialysis before the follow-up assessment; acute renal failure; history of kidney transplant
 10. Any history of a malignancy other than basal cell carcinoma within the past 5 years
 11. Clinically significant unstable neurologic, ophthalmologic, hepatobiliary, respiratory, or hematologic illness or unstable cardiovascular disease (eg, severe hypotension, uncontrolled cardiac arrhythmia, or myocardial infarction) within 12 months prior to screening
 12. Pregnancy or breast feeding or intent to become pregnant during the study period
 13. Known hypersensitivity to $\alpha_2\delta$ ligands or other components of the study medications. Note: Prior exposure to DS-5565 is allowed, as long as hypersensitivity to DS-5565 was not observed.
 14. Clinically significant ECG abnormalities at the Screening Visit
 15. Subjects who are at risk of suicide, as defined by their responses to the C-SSRS or in the opinion of the Investigator. Note: Subjects answering "yes" to any of the C-SSRS questions must be excluded. Such subjects should be referred immediately to a mental health professional for appropriate evaluation.

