1.1.3. Intended Use Under Investigation

DS-5565 is being developed as treatment for diabetic peripheral neuropathic pain (DPNP), fibromyalgia (FM), and post-herpetic neuralgia (PHN).

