1.2. Study Rationale

Several classes of medications, including anticonvulsants, tricyclic antidepressants, serotonin-norepinephrine reuptake inhibitors (SNRIs), and opioids are used to treat the symptoms of FM, with variable efficacy, safety, and tolerability. Currently available $\alpha_2\delta$ ligands, gabapentin and pregabalin, are established as effective treatments for pain associated with diabetic peripheral neuropathy.^{2,3} In addition they are approved for the treatment of pain in FM in the USA and some other countries, however not in the EU (European Union). The dosage, and thus efficacy, of these agents are limited by frequent and significant CNS-related side effects, including dizziness and somnolence; associated weight gain and peripheral edema can also be problematic.⁴ As a result, a large proportion of patients with FM are left with insufficient pain relief and new treatment options are needed.

DS-5565 is an oral analgesic drug being developed by Daiichi Sankyo for DPNP, FM, and PHN, globally. This study is being conducted in patients with chronic renal dysfunction and pain due to fibromyalgia solely, after receiving guidance from the US FDA. DS-5565 binds to the $\alpha_2\delta$ subunit of voltage-dependent calcium channels, the main target for the analgesic effect of pregabalin and gabapentin. Nonclinical and Phase 1 and Phase 2 clinical data support the progress of DS-5565 into Phase 3 studies of FM to evaluate the effect of DS-5565 on ADPS as compared to placebo during the course of a 13-week (stable dose, not including 1 week of titration for the DS-5565 15 mg BID group) double-blind treatment period.

DS-5565 has been studied in subjects with renal dysfunction. Study DS5565-A-E106 evaluated the pharmacokinetics and safety of a single 5 mg dose in 40 subjects (8 normal renal function and 8 each with mild, moderate, severe, and ESRD requiring hemodialysis). Pharmacokinetics of DS-5565 and its lactam metabolite were evaluated over a 72-hour period. For the analysis, the groups were analyzed by normal creatinine clearance (CrCl) (≥ 90 mL/min), mild reduction in CrCl (60 to 89 mL/min), moderate reduction in CrCl (30 to 59 mL/min), and severe reduction in CrCl (15 to 29 mL/min as per the FDA Draft Guidance, *Pharmacokinetics in Patients with Impaired Renal Function — Study Design, Data Analysis, and Impact on Dosing and Labeling*.⁵

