7.2.1. Average Daily Pain Score

ADPS will be calculated by averaging up to 7 available pain scores. Pain scores will be recorded in a daily diary using an 11-point NRS ranging from 0 (no pain) to 10 (worst possible pain). Every morning upon awakening, prior to taking study medication, the subject will circle the number (0 to 10) that best describes the worst pain over the previous 24 hours.⁶ The diary will be completed every morning upon awakening from the start of the baseline period (Day -6) through the morning following the last day of study drug administration. Baseline ADPS will be calculated as the average of the last 7 available pain ratings obtained during the Baseline Period, including the final rating on the morning prior to randomization (a minimum of 4 daily pain ratings will be required as an inclusion criterion). During the treatment period, weekly ADPS will be determined at the end of each week based on all available daily pain scores for the prior week.

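### Exclusions 6 and 7 are written around neuropathic pain, so a fibromyalgia subject with a stable painful neuropathy can enter and score that pain on the ADPS

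*Combined protocol and SAP*

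**What the plan says.** Section 1.2 fixes the indication: "This study is being conducted in patients with chronic renal dysfunction and pain due to fibromyalgia solely".

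Two exclusions in section 4.1.2 deal with competing conditions, and both take neuropathic pain as the reference:

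- Exclusion 6: "Significant neurological or psychiatric disorder unrelated to neuropathic pain".
- Exclusion 7: "Other severe pain (eg, sciatica, rheumatoid arthritis) that might impair the assessment of neuropathic pain".

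The synopsis has the same text, including the phrase "might impair the assessment of neuropathic pain". Section 5.2.1, below Table 5.1, also labels the non-drug therapies it prohibits as therapies for neuropathic pain.

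The pain measure names no source. Under section 7.2.1 the subject picks the number that "best describes the worst pain over the previous 24 hours". That score sets the entry threshold (ADPS of at least 4, inclusion 6) and is the secondary efficacy endpoint (section 3.1.3).

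**The concern.** An exclusion for competing pain should protect the pain under study. Here it protects a different one. Painful diabetic neuropathy and post-herpetic neuralgia are the drug's other two target indications (section 1.1.3), so the pain that could slip in may itself respond to treatment. If a subject's worst pain is neuropathic, both that subject's qualification on ADPS and the later change from baseline may reflect the neuropathy. Any resulting contrast would still be reported as a result in FM. With about 100 sites planned for about 60 subjects (synopsis), one cannot rely on every site reading the intended meaning into the text.

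**Working it through.** **Step 1: does an entry path exist?** Take a subject who meets the FM criteria and has a stable, painful neuropathy.

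| Criterion | Catches this subject? |
|---|---|
| Exclusion 6 | No. The disorder is related to neuropathic pain, so it is exempt. |
| Exclusion 7 | Not on a literal reading. The neuropathic pain is the pain being protected. Sciatica is a named example, so some nerve pain is excluded. |
| Inclusion 5d: "The subject does not have a disorder that would otherwise explain the pain" | Not clearly. It belongs to the FM diagnosis, and a localized neuropathy leaves widespread pain with 11 of 18 tender points unexplained. |
| Exclusion 11: "Clinically significant unstable neurologic, ophthalmologic, hepatobiliary, respiratory, or hematologic illness" | No, if the neuropathy is stable. |
| Exclusions 1 and 2, Table 5.1 | Only if the subject needs ongoing pain medication or cannot wash out. |

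The path is therefore open, but only for subjects who can do without prohibited analgesics.

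**Step 2: numbers available.** The only sample-size figure reproduces: 60 x (1 - 0.25) = 45 completers (section 11.11). At 2:1 this is about 40 v 20 randomized and 30 v 15 completing. The protocol gives no SD, target difference or power.

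**Step 3: distortion of the ADPS contrast.** Let p be the share in each arm (assumed equal) whose score tracks neuropathic pain, d_N the treatment effect on that pain and d_F the effect on FM pain.

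- Observed contrast = p x d_N + (1 - p) x d_F
- Distortion = observed contrast - d_F = p x (d_N - d_F)

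For d_N, section 1.1.5 gives two Phase 2 results in diabetic peripheral neuropathic pain (DPNP) at 15 mg BID: -1.01 (US study, Week 5) and -0.30 (Asian study, Week 7, not significant). This dose is the relevant reference because the trial's doses are predicted to give similar exposure (sections 1.2 and 3.2.1). Setting d_F = 0 and p = 10% to 30%, both assumptions:

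| p | d_N = -0.30 | d_N = -1.01 |
|---|---|---|
| 10% | -0.03 | -0.10 |
| 20% | -0.06 | -0.20 |
| 30% | -0.09 | -0.30 |

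If d_F equals d_N the distortion is zero. If the FM effect is the larger, the distortion changes sign.

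**Step 4: scale.** For an assumed SD of 1.5 to 2.5, the 95% half-width is 1.96 x SD x sqrt(1/n1 + 1/n2).

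- All randomized, 40 v 20: 0.81 to 1.34 points.
- One stratum under an assumed even split, 20 v 10: 1.14 to 1.90 points.

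Section 11.4.2 calculates its intervals within stratum, so the second line is the relevant one. The largest distortion in the table, 0.30, is well inside either interval.

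**Step 5: chance imbalance.** One subject whose change differs by an assumed 1 to 3 points moves the mean of 15 placebo completers by 1/15 to 3/15, or 0.07 to 0.20. In a half-size stratum (7.5 placebo completers) the shift is 0.13 to 0.40.

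**The case against.** The strongest case on the other side is that this is a slip of wording with little consequence. Several parts of it stand:

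- Exclusions 1 and 2 and Table 5.1 keep out anyone whose neuropathy needs regular treatment, and acetaminophen is the only rescue medication (section 5.2.2).
- Naming sciatica suggests the authors did not mean to spare all nerve pain. Many investigators will read other severe pain as any pain other than FM.
- This is a safety study. It has no primary efficacy endpoint (section 7.1), and ADPS is only compared numerically with confidence intervals. The secondary objective in section 2.1.2 does not itself attribute the pain to FM, and PGIC rates overall status.

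These points limit the consequences. They do not correct the text, because none of them makes FM pain the reference in exclusions 6 and 7.

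A reader might infer two stronger things that the protocol does not support. One is that such subjects would drive the ADPS result. That is possible for a subject's own score, but the group effect depends on a share the protocol does not give. Quoting only the US Phase 2 effect would also leave out the smaller, non-significant Asian results (-0.30 to -0.42). The other is that pre-existing neuropathy spoils the neurological examination as a safety endpoint. That endpoint is change from baseline (section 3.1.3), and the examination is done at screening, at randomization and at each clinic visit through end of treatment (Table 17.1), so existing deficits are recorded before dosing.

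**Conclusion.** The inconsistency is real and sits in operative eligibility text. Exclusions 6 and 7, in section 4.1.2 and the synopsis, and the therapy restriction in section 5.2.1 name the wrong index pain for an FM trial. On a literal reading they leave a narrow entry path for subjects with a stable painful neuropathy.

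The likely numerical effect is small: about -0.03 to -0.30 ADPS points. That range rests on an assumed share of 10% to 30% in each arm, no effect on FM pain, and DPNP effects carried over from Phase 2 studies of 5 and 7 weeks. The true size cannot be obtained from the protocol. The primary safety objective and the sample size are untouched.

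It does not follow that the diary must ask for pain due to FM. Whether patients can separate their sources of pain is a measurement question the protocol does not settle, and the eligibility correction stands without it.

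**What to change.** In exclusion 7, in section 4.1.2 and the synopsis, change the protected assessment from neuropathic pain to fibromyalgia pain, so that a severe painful neuropathy counts as other severe pain. Reconcile the neuropathic-pain wording of exclusion 6 and of the non-pharmacological restriction in section 5.2.1 with the FM indication. For exclusion 6, the sponsor should decide deliberately how wide it is to be: simply substituting fibromyalgia would take in significant neurological disorders whether or not they are painful.

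The cost is a wording amendment and a slightly smaller eligible pool. For exclusion 7 the loss is confined to subjects with severe competing pain. The protocol gives no figure from which to estimate it, and recruitment is already thin at about 100 sites for 60 subjects. No endpoint, analysis or sample-size figure changes.
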